Basic Information

1. * Title of study:

Impact of Theraworx Foam on Pain and Motion and Patient-Reported Outcomes in Thumb Arthritis

2. * Short title:

Theraworx Foam

3. * Brief description:

Thumb carpometacarpal osteoarthritis (CMC OA) affects up to 33% of people over the age of 40, which leads to inflammation, pain, and weakness of the CMC joint.

Treatment modalities are both conservative and surgical with surgical options including osteotomy,

bone excision, ligament reconstruction, and various prosthetic implants. The conservative treatment options, however, are limited to NSAIDs and bracing or steroid injections.

Advances in topical therapies have the potential to deliver focused treatment to the CMC joint. Novel treatment of inflammation can potentially reduce inflammation and pain associated with progressing osteoarthritis. Theraworx Relief is an FDA registered foam that has theoretical impact on inflammation reduction in human subjects treated with the topical foam.

This pilot study seeks to investigate potential benefit in the use of Theraworx Foam in patients diagnosed with thumb CMC OA. Patients presenting to our upper extremity orthopedic surgery clinic for thumb/hand/wrist pain will be diagnosed by a Board Certified Hand

Surgeon as per standard protocols. Patients who are recommended to follow a conservative treatment modality and are interested in participating in this study will be randomized into treatment or control groups. Both groups will undergo symptom assessment, strength testing, and range of motion testing prior to starting the

standard

conservative treatment of bracing. The treatment group will use the TheraWorx topical foam and the compression wrap nightly for 2 weeks for at least 6 hours per night. Control group will use a compression wrap for the same time period. Both groups will return at 1 and 2 weeks for repeat strength and range of motion testing and symptom assessment.

4. * Principal investigator:

[name]

5. * Does the investigator have a financial interest related to this research?

Yes No

6. * Will an external IRB act as the IRB of record for this study?

Yes No

7. * What kind of study is this?

Single-site study

8. Attach the protocol:

- Sponsor/Multicenter protocol
- Investigator-initiated protocol
- Emergency Use Consent/ Protocol/ FDA Form 3926
- [Exempt Application form](#)

Document Category Date Modified Document History

There are no items to display

Study Aims

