Significance: If the Theraworx foam and/or Theraworx foam with compression wrap can be shown to reduce pain and allow for improved functional measures, the product can be proposed as an option for conservative treatment of thumb CMC OA and reduce the reliance on oral pain medications, steroid injections, and surgery.

Study Design

1. Total number of subjects to be enrolled at this site (enter -1 for chart reviews, banking, registries):

60

2. Describe and explain the study design:

After informed consent, subjects will be randomized to one of three groups:

1. Theraworx foam with compression wrap
2. Placebo foam with compression wrap
3. Theraworx foam alone

Baseline testing will include Numeric Pain Rating Scale (NPRS). The Disabilities of the Arm, Shoulder, and Hand (DASH) will be administered to the participant by the study coordinator. Static range of motion will be tested with a wrist goniometer measuring flexion, extension, ulnar deviation, and radial deviation with the participant's elbow supported on a hand table. Strength testing will be performed with a hand dynamometer and pinch meter. These questionnaires/tests will be performed at baseline, 1 week, and 2 week visits. They should take approximately 10 minutes to complete.

Subjects will be instructed to apply the foam every night (two pumps and rub into the base of the thumb). This will be demonstrated by the research coordinator (to be hired and added to this IRB application).

Participants will be asked to apply the foam nightly for a minimum of 6 and maximum 10 of hours and avoid use of lotions, topical creams, or topical NSAIDs during the study period. Subjects will be advised to avoid other oral prescription or OTC pain relief medications during the 2-week study period. A study data sheet will be given at this time for the participant to document nightly compliance hours, daily Tylenol use, and daily pain rating. This sheet will be collected at the 2 week visit. This portion of the research visit should take approximately 5 minutes but will allow for time for questions.

Randomization will occur via block randomization designed to randomize subjects into groups that result in equal sample sizes.

3. Describe the primary and secondary study endpoints:

All endpoints are primary:

1. Numeric Pain Rating Scale
2. Disabilities of the Arm, Shoulder, and Hand (DASH)
3. Pinch strength
4. Grip strength
5. Thumb range of motion

4. Provide a description of the following study timelines:

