Screening and Enrollment: Patients diagnosed with thumb CMC OA by the PI and recommended for participation in the study will be assessed for inclusion and exclusion criteria appropriateness by the study coordinator. If they are candidates, consent will be obtained by the PI in a private room and they will be randomized into treatment or control group by the coordinator. At this time, the x-ray taken during routine care by the PI for diagnosis will be obtained and graded for severity.

Demographic information including age and gender will also be collected.

Research Visits: Baseline, 1 week and 2 week visits

Study procedures will be performed by the study coordinator in a patient room equipped with a hand table, if necessary, patient will be moved to an procedure room similarly equipped. Numeric Pain Rating Scale (NPRS), and Disabilities of the Arm, Shoulder, and Hand (DASH) will be administered to the participant by the study coordinator. Static range of motion will be tested with a wrist goniometer measuring flexion, extension, ulnar deviation, and radial deviation with the participant's elbow supported on a hand table. Strength testing will be performed with a hand dynamometer and pinch meter. These questionnaires/tests will be performed at the baseline, 1 week and 2 week visits. They should take approximately 10 minutes to complete. Study coordinator will also provide the participant with the foam and compression wraps and provide instructions for its use. The compression wrap is a cloth wrap (similar to an elastic bandage wrap) that will be saturated/treated with the Theraworx foam. Participants will be asked to apply the foam treated wrap nightly for a minimum of 6 and maximum 10 of hours and avoid use of lotions, topical creams, or topical NSAIDs during the study period. A study data sheet will be given at this time for the participant to document nightly compliance hours, daily Tylenol use, and daily pain rating. This sheet will be collected at the 2 week visit. This portion of the research visit should take approximately 5 minutes but will allow for time for questions.

- 2. Upload a copy of all materials used to collect data about subjects: (Attach all surveys, interview/focus group scripts, and data collection forms except for case report forms, SCID or KSADS):**

Data

Collection

10/9/2018 History

Data

Collection

10/9/2018 History

Data

Collection

9/30/2018 History

3. * Will blood samples be obtained for research purposes? Yes No

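### Baseline is described as taken after randomisation by the coordinator who randomises, so any analysis of improvement rests on a baseline that allocation could influence; the SAP's 2-week ANOVA is not affected

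*Combined protocol and SAP*

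**What the plan says.** Three places describe the start of the trial.

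- **Research Activities, item 1.** Under Screening and Enrollment, the PI obtains consent from suitable patients and "they will be randomized into treatment or control group by the coordinator". The research visits, including baseline, come next: "Study procedures will be performed by the study coordinator in a patient room equipped with a hand table". Supplies follow the tests: "Study coordinator will also provide the participant with the foam and compression wraps and provide instructions for its use".
- **Study Design, item 2.** "After informed consent, subjects will be randomized to one of three groups". The three arms are listed, and the text then continues with "Baseline testing will include Numeric Pain Rating Scale (NPRS", DASH, goniometry and strength testing.
- **Basic Information, item 3.** Patients are randomised, and then "Both groups will undergo symptom assessment, strength testing, and range of motion testing prior to starting the" conservative treatment. The groups already exist at testing; only the start of treatment is explicitly placed after it.

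One arm receives "Placebo foam with compression wrap", and the third receives active foam without a wrap. Block randomisation to equal groups is stated. The documents do not mention concealment of the sequence, coded supplies or masking of anyone.

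All four hypotheses (Study Aims, item 1) are about improvements. The SAP names the 2-week pain score as primary and analyses it by ANOVA, with no change score or baseline covariate. Secondary outcomes are also by ANOVA, and the SAP does not say whether level or change is analysed.

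**The concern.** A baseline is useful in a randomised comparison because it cannot depend on the arm. That is guaranteed only if it is recorded before anyone involved in the measurement knows the assignment. Here one role allocates the patient, administers two questionnaires, reads a goniometer and runs effort-dependent strength tests, in that order as described. If knowledge of the arm changes how questions are put or how effort is encouraged, the recorded baseline can differ by arm for reasons unrelated to the patients.

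At stake is any result expressed as improvement: change scores, baseline-adjusted comparisons, and the table used to judge whether the arms were comparable at entry. A baseline recorded before allocation cannot be recreated at analysis.

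**Working it through.** **1. Is the order really randomise-first?** Research Activities item 1 is the strongest evidence, because it puts randomisation in the enrolment step and baseline in the research visits that follow. Study Design item 2 and Basic Information item 3 agree. None of the three states the order as a rule, and none contradicts it.

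**2. Who can know the arm at baseline?** The coordinator randomises. Anyone who sees the full assignment can tell the no-wrap arm from the two wrap arms. Active and placebo foam could be indistinguishable under coded supply, but no coding is described. Each hypothesis compares foam plus wrap with foam alone as well as with placebo foam plus wrap, so each contains at least one contrast that is open in this way. Supplies are handed over after testing, so the participant need not know the arm yet.

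**3. The plan's own figure, used only to set a scale.** Study Design item 8 gives a difference of 2 points, alpha 0.05, power 0.80, 16 per group, and no SD. With a two-sided normal approximation, n = 2(1.960 + 0.842)² × SD²/2². Setting n = 16 gives SD = 2/(2.802 × √(2/16)) = 2.02. With SD 2.0, n = 15.7, rounded up to 16 (a t-test calculation gives 16.7, so 17). Drop-out: 16/(1 − 0.20) = 20, and 3 × 20 = 60, as stated. The point does not depend on these figures.

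**4. Where a baseline shift goes.** Let τ be the true difference between two arms at 2 weeks, b the shift in recorded baseline caused by allocation, and β the within-arm slope of follow-up on baseline.

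- 2-week score: expected difference = τ. No baseline enters.
- Change score: τ − b.
- Baseline-adjusted: τ − βb.

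For scale, an assumed b of 0.3 to 0.5 points is 0.3/2 = 15% to 0.5/2 = 25% of the 2-point effect in a change score. With an assumed β of 0.5 it is 0.15 to 0.25 points after adjustment.

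**5. Simulation.** Assumptions: two arms of 16, SD 2 at both times, τ = 0, two-sided 5% tests, 5,000 runs per row (simulation standard error near 5% is √(0.05 × 0.95/5000) = 0.3 percentage points). Entries are bias and type I error.

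| Shift b | Correlation | 2-week score | Change score | Baseline-adjusted |
|---|---|---|---|---|
| 0.5 | 0.3 | 0.009, 4.9% | −0.494, 9.3% | −0.143, 5.3% |
| 0.5 | 0.5 | −0.011, 5.3% | −0.513, 10.8% | −0.259, 6.9% |
| 0.5 | 0.7 | 0.009, 5.5% | −0.495, 14.0% | −0.342, 9.6% |
| 1.0 | 0.3 | −0.008, 5.1% | −1.013, 21.4% | −0.308, 7.5% |
| 1.0 | 0.5 | −0.008, 4.7% | −0.995, 27.7% | −0.503, 11.6% |
| 1.0 | 0.7 | −0.004, 5.1% | −1.002, 43.1% | −0.700, 25.4% |

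With b = 0, all three analyses have bias within 0.013 of zero and type I error of 4.5% to 5.5%. The simulation matches the algebra: the 2-week comparison is untouched, the change score takes the whole shift, and the adjusted estimate takes about correlation × b.

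**The case against.** The strongest objection is that the SAP's primary analysis uses no baseline. A reader might infer from the sequence that the primary result is biased. The documents do not support that: an ANOVA of the 2-week score is unaffected by a shifted baseline, as the table shows. This part of the objection stands in full.

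A reader might also infer that the coordinator, or the participant, does know the arm at baseline. That goes beyond the text. Randomising a patient does not show what the coordinator sees, a placebo foam exists, and foam and wraps are described as handed over after the tests. What remains is that nothing described prevents the coordinator from knowing.

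The order is also read from narrative. Study Design item 2 is not strictly chronological, since its block-randomisation sentence comes last. That lowers confidence in the reading but does not reverse it.

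Two further inferences add little. Severity grading takes place at enrolment ("At this time, the x-ray taken during routine care by the PI for diagnosis will be obtained and graded for severity"), but the film predates allocation, and the grade is neither an endpoint nor a covariate. A participant who left on learning the arm would have no baseline, but would have no 2-week score either.

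Finally, the shift requires someone unmasked. If the coordinator is unmasked, the same role also takes the 2-week measurements, which bears directly on the primary outcome. Reordering does not cure that; it is a separate issue.

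**Conclusion.** The point holds as a limited one. As described, randomisation by the coordinator precedes baseline testing by that coordinator, with no masking or concealment, so baseline values are not protected from influence by allocation. The SAP's primary comparison is not biased by this. Exposed are any change-score or baseline-adjusted analysis of the improvements in hypotheses 1a to 2b, and the baseline comparability table.

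Neither the size nor the direction of a shift can be found from the documents. The figures of 9–14% and 5–10% for a 0.5-point shift, and 21–43% and 8–25% for a 1.0-point shift, show sensitivity under an assumed shift, SD 2 and correlations of 0.3 to 0.7. They do not predict what will happen in this trial. The change is worth making because it costs so little.

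**What to change.** In Basic Information item 3, Study Design item 2 and Research Activities item 1, state one explicit order:

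1. consent;
2. eligibility check;
3. baseline NPRS, DASH, motion, grip and pinch completed and recorded;
4. randomisation assignment revealed;
5. foam and wrap dispensed, with instruction.

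All steps stay in the same visit, with the same staff and tests. The sample size and the SAP's primary analysis do not change, so the cost is a wording amendment. It protects the baseline whatever is decided about masking, but it does not address masking of the 1- and 2-week assessments, which needs its own answer.

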Duration of an individual subject's active participation:

2 weeks

Duration anticipated to enroll all subjects:

1 year

Estimated date for the investigator to complete this study (complete primary analyses):

9/30/2019

5. List the inclusion criteria:

Patients of [name], the PI, with the following:

1. Thumb CMC arthritis
2. greater than or equal to age 18
3. Interested in non-operative treatment of thumb arthritis

6. List the exclusion criteria:

1. Recent corticosteroid injection into the thumb joint
2. Non-English speaking
3. skin lesions or rashes on the thumb
4. current use of topical anti-inflammatory medications
5. concomitant thumb/wrist diagnoses that would impact the results (as determined by the PI)
6. known allergy to magnesium

7. Will children or any gender, racial or ethnic subgroups be explicitly excluded from participation?

Yes No

* Identify the subgroups and provide a justification:

Children - arthritis of the thumb CMC joint does not typically exist in subjects less than the age of 18 and including a rare patient that might have CMC arthritis would bias our results.

8. Describe the power analysis used and cite your method of statistical analysis. If a power analysis is not possible, thoroughly justify the sample size required for the study, including appropriate literature citation (alternatively provide page reference in attached protocol):

The mean pain reported in subjects with CMC arthritis is 5 (out of 10) on the numeric pain rating scale. Assuming a clinical meaningful change in pain of 2 on this scale, an alpha of 0.05 and beta of 0.2, the power analysis demonstrates 16 subjects required per group. Assuming a drop out rate of 20%, we will enroll 20 subjects per group.

Research Activities

- 1. * Provide a detailed description of all research activities (including screening and follow-up procedures) that will be performed for the purpose of this research study. This description of activities should be complete and of sufficient detail to permit an assessment of associated risks.**

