9. Describe the planned involvement of a 'contact person' who interacts with the subject on a regular basis and who will notify the investigators immediately of any problems related to the subject's disease or condition:

There is no reason why the subject could not contact the investigators in this study on thumb arthritis. No plans to involve a contact person.

Note: The involvement of the contact person must also be addressed in the consent form

Statistical Analysis Plan

The Primary Outcome is VAS pain score at 2 weeks

This will be analyzed with ANOVA which is the appropriate test for continuous data and multiple groups.

Significance will be set at 0.05

Secondary Outcomes

Will also be analyzed using ANOVA.

Significance will be set at 0.05

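### The x-ray severity grade is collected but used neither in the randomisation nor in the ANOVA: a missed gain in precision, not a bias

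*Combined protocol and SAP*

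**What the plan says.** **Collection of the grade.** Under Research Activities, item 1 (Screening and Enrollment), candidates give consent, then "they will be randomized into treatment or control group by the coordinator", and at that point "the x-ray taken during routine care by the PI for diagnosis will be obtained and graded for severity". The film predates consent, but the text lists the grading after the allocation. It does not state the grading scale, who grades, whether the grader is blind to arm, or what the grade is for.

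**Randomisation.** Study Design, item 2: "After informed consent, subjects will be randomized to one of three groups". The method is given in one sentence: "Randomization will occur via block randomization designed to randomize subjects into groups that result in equal sample sizes". No stratification factor is named.

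**Analysis.** In the Statistical Analysis Plan, "The Primary Outcome is VAS pain score at 2 weeks", and "This will be analyzed with ANOVA which is the appropriate test for continuous data and multiple groups". Of the secondary outcomes it says "Will also be analyzed using ANOVA". No covariate, baseline adjustment or change score is mentioned.

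**Eligibility.** The inclusion and exclusion criteria (Study Design, items 5 and 6) set no radiographic severity limit, so mild and advanced disease can both enter.

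**The concern.** A severity measure is recorded on every participant, and the trial is small enough for the arms to differ on it noticeably by chance. The analysed outcome is the pain score at 2 weeks with no adjustment, so nothing else in the model would absorb such a difference if severity is related to pain.

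Two things are at stake. If grade predicts the outcomes, the variance it explains is left in the error term and power is lost. And if the baseline table shows the arms to differ on grade, the plan offers no pre-specified response, so any adjustment would be chosen after seeing the data.

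**Working it through.** **Inputs from the documents.** Three equal arms; 20 enrolled and 16 evaluable per arm; 20% dropout; a 2-point difference in pain; alpha 0.05 and beta 0.2 (Study Design, item 8: "Assuming a clinical meaningful change in pain of 2 on this scale, an alpha of 0.05 and beta of 0.2").

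**Assumptions, because the documents give no figure.** SD of pain 2; two-sided test; half of participants severe (30% as a variant); grade explaining 4%, 9% or 16% of the variance of 2-week pain. The pain scale in the Statistical Analysis Plan is taken to run 0 to 10, like the scale in item 8.

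**1. The plan's own sample size.** No SD is stated, so 16 cannot be reproduced from stated inputs alone. With SD 2, the two-sided normal approximation gives n = 2 × [2 × (1.960 + 0.842) / 2]² = 15.7, so 16. An SD from 1.96 to 2.02 gives 16, which is why SD 2 is used here. The dropout step reproduces exactly: 16 / (1 − 0.20) = 20.

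**2. Chance imbalance in severe share, no stratification.** The arm counts are independent Binomial(20, p). A 25-point difference is 5 participants of 20.

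| Severe share p | One given pair | Any of the three pairs |
|---|---|---|
| 0.5 | 15.4% | 32.7% |
| 0.3 | 11.9% | 26.3% |

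**3. What such an imbalance does to a contrast.** If severe disease carries 1.5 points more pain (assumption), the realised shift is 0.25 × 1.5 = 0.375 points, about a fifth of the 2-point target. With half severe and SD 2, that gap implies R² = (1.5/2)² / 2² = 0.5625/4 = 14%, near the top of the assumed range. At R² = 4%, the gap is 2 × √(0.04 × 4) = 0.8 points and the shift 0.25 × 0.8 = 0.2, a tenth of the target. The standard error of the contrast at 20 per arm is 2 × √(2/20) = 0.63, so the 0.375 shift is about 0.6 of one standard error.

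**4. Power for one contrast, 16 evaluable per arm.** Residual SD = 2 × √(1 − R²); noncentrality = 2 / [residual SD × √(2/16)]; two-sided noncentral t, with 48 − 3 = 45 error degrees of freedom unadjusted and 44 with grade in the model.

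| Model | Residual SD | Noncentrality | Power |
|---|---|---|---|
| No covariate | 2.000 | 2.83 | 79.0% |
| Grade, R² 4% | 1.960 | 2.89 | 80.6% |
| Grade, R² 9% | 1.908 | 2.96 | 82.6% |
| Grade, R² 16% | 1.833 | 3.09 | 85.5% |

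If grade explains nothing, the lost degree of freedom costs about 0.04 percentage points of power.

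**5. Grade after baseline pain.** Assume correlations of 0.5 (baseline with week-2 pain), 0.3 (grade with week-2 pain) and 0.3 (grade with baseline). Baseline alone explains 0.5² = 25%. Both together explain (0.25 + 0.09 − 2 × 0.5 × 0.3 × 0.3) / (1 − 0.09) = 0.25/0.91 = 27.5%. Grade therefore adds about 2.5%, against 0.3² = 9% on its own.

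**6. Validity of the planned test.** In 10,000 simulated trials per setting (16 per arm, overall F test, half severe), r is the correlation of severity with pain:

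| Allocation and model | Type I error, r = 0.3 | Type I error, r = 0.5 |
|---|---|---|
| Unstratified, plain ANOVA | 0.050 | 0.051 |
| Unstratified, grade in model | 0.049 | 0.050 |
| Stratified, plain ANOVA | 0.042 | 0.018 |
| Stratified, grade in model | 0.055 | 0.049 |

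The planned combination holds its level. Stratifying and then leaving the stratum out of the model is conservative.

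**The case against.** The strongest reply is that nothing here is an error. Chance imbalance is part of the sampling variation that the ANOVA error term already measures. Stratification and covariate adjustment are efficiency choices, and the plan never promises to use the grade. It sits beside age and gender at enrolment, which fits a purely descriptive purpose. No passage links x-ray grade to 2-week pain, so every figure for the size of the gain rests on assumption. Baseline pain, DASH, strength and motion are also measured and also absent from the model, and the baseline value of the outcome is the more natural first covariate.

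Most of this stands. A reader might infer that unequal severity would bias the comparison or inflate type I error. The documents do not support that: allocation is randomised, and the check in step 6 shows the planned test at its nominal level. A reader might also take the 33% as the risk to a particular comparison; it covers any of three pairs, and for one given pair the figure is 15%.

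What the reply does not remove is that the grade is already collected, costs almost nothing to include, and has no stated use. If grade was meant only for description, the plan should say so.

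**Conclusion.** The point holds as a minor, optional improvement in precision and pre-specification. The planned ANOVA is valid without it. The gain for one contrast is about 1.6 to 6.5 percentage points of power (80.6 − 79.0 to 85.5 − 79.0) if grade explains 4% to 16% of week-2 pain variance, and less once baseline pain is in the model. This rests on an assumed SD of 2, 16 evaluable per arm, and a grade–pain relation that the documents do not give; confidence in the size is therefore low. The imbalance figures further assume that about half the participants are severe.

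**What to change.** In the Statistical Analysis Plan, replace the plain ANOVA with an ANCOVA for the primary and secondary outcomes that includes the baseline value of the outcome and, second, a two-level x-ray severity grade. Name the grading scale and the cut-point in advance. Have the grade read before allocation, or by someone blind to arm.

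Optionally, since the film exists before randomisation, run the blocks within the same two levels. In that case the grade must be read before allocation, the enrolment text must put grading ahead of randomisation, and the stratum must be in the model, because of the conservatism shown in step 6.

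The grade costs one degree of freedom, as does the baseline term. Stratifying also needs a second randomisation list. If grade is only weakly related to the outcomes, adding it will gain little; the baseline adjustment should come first in any case.

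### The visit instructions under Research Activities do not follow the three-arm design: the foam-alone arm is not exempted from the wrap, and the method of applying the foam differs from Study Design

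*Combined protocol and SAP*

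**What the plan says.** Study Design, item 2, is explicit: "After informed consent, subjects will be randomized to one of three groups". The list that follows is Theraworx foam with wrap (arm 1), "Placebo foam with compression wrap" (arm 2) and Theraworx foam alone (arm 3). Study Aims, item 1 (hypotheses 1a to 2b) and Placebo Arm, item 4, use the same three arms. On use of the product, Study Design says: "Subjects will be instructed to apply the foam every night (two pumps and rub into the base of the thumb".

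Research Activities, item 1, describes what happens at visits. Of eligible patients it says "they will be randomized into treatment or control group by the coordinator". On supplies: "Study coordinator will also provide the participant with the foam and compression wraps and provide instructions for its use". On the wrap: "The compression wrap is a cloth wrap (similar to an elastic bandage wrap) that will be saturated/treated with the Theraworx foam". On use: "Participants will be asked to apply the foam treated wrap nightly for a minimum of 6 and maximum 10 of hours". It mentions neither placebo foam nor a foam-alone arm, and nothing in it limits the wrap to particular arms.

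The brief description (Basic Information, item 3) also has two groups: foam plus wrap, and a control group with the wrap only and no placebo foam.

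**The concern.** Each of the four hypotheses sets arm 1 against two comparators. Arm 1 versus arm 2 isolates the foam, since both wear a wrap. Arm 1 versus arm 3 isolates the wrap, since both use Theraworx. Each contrast is interpretable only if the two arms differ in that one component.

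The form asks for a complete and detailed account of activities under Research Activities, so that section should be usable as the operating instruction. Study Design notes that the coordinator, who will randomise, supply and instruct participants, had yet to be hired, so that person would rely on written procedures. If the visit text governed what is handed out, arm 3 could be given a wrap and would no longer differ from arm 1.

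The application method raises a second problem. One section has foam rubbed into the skin; the other has a wrap saturated with foam. The text does not say whether one replaces the other or whether both apply. If arm 1 used a saturated wrap and arm 3 rubbed the foam in, the contrast meant to isolate compression would also carry a difference in delivery, and perhaps in dose.

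**Working it through.** **Step 1. Which design is intended?** Inputs: 16 required per group and 20% dropout (Study Design, item 8); 60 in total (Study Design, item 1). The plan states: "Assuming a drop out rate of 20%, we will enroll 20 subjects per group".

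- Enrolment per group = 16 / (1 − 0.20) = 20, as stated.
- Number of groups = 60 / 20 = 3.
- A two-group trial would enrol 2 × 20 = 40, which does not match the stated total.

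The arithmetic agrees with the three-arm list. The 16 is taken as given. It depends on a standard deviation that the plan does not state, but nothing here turns on it.

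**Step 2. Compare the two sections arm by arm.**

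| Arm in Study Design, item 2 | What that section implies | What Research Activities, item 1, gives if applied to everyone | Match? |
|---|---|---|---|
| 1. Theraworx foam + wrap | two pumps rubbed in, plus wrap | foam, plus a Theraworx-treated wrap | arm agrees; method differs |
| 2. Placebo foam + wrap | placebo rubbed in, plus wrap | foam (product not named), plus a wrap described only as Theraworx-treated | ambiguous |
| 3. Theraworx foam alone | two pumps rubbed in, no wrap | foam, plus a Theraworx-treated wrap | conflicts |

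**Step 3. Consequence for the contrasts.**

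- Arm 1 versus arm 3, as designed: (foam + wrap) − (foam) = wrap.
- With a wrap also given to arm 3: (foam + wrap) − (foam + wrap) = no difference in treatment.
- With a saturated wrap in arm 1 and rubbed-in foam in arm 3: the difference is wrap plus delivery method, and the two cannot be separated.
- Arm 1 versus arm 2 is unaffected as long as the placebo arm's wrap carries placebo foam or no foam.

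**Step 4. Extent.** The direct conflict concerns one arm, 20 / 60 = 33% of planned enrolment. This is the size of the arm. It does not estimate how many would be treated wrongly or how large any bias would be; the documents give no basis for either.

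**The case against.** The strongest reply is that the intended design is not in doubt. Three sections and the sample size agree on three arms, the significance paragraph under Study Aims distinguishes foam from foam with wrap, and Study Design gives a foam instruction that works in every arm. Moreover, read literally, Research Activities has no third arm at all. A coordinator would learn of arm 3 only from Study Design, where its label already says that the foam is used alone. Giving that arm a wrap would mean using one section for allocation and disregarding its label when handing out supplies. Monthly meetings (Data Safety and Monitoring, item 1) are to verify compliance and testing procedures.

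Much of this stands. It is why the outcome is something that could happen, not something that would. The two-group phrase in the screening paragraph is also weak evidence by itself, because it may be shorthand for one test arm and its comparators. The meetings are not described as a check on what each arm is supplied. Nor does a clear intention make the operating text right: its wrap instruction has no exception for arm 3, and the label of arm 3 does not settle how foam is to be applied in arms 1 and 2.

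A reader might go further and infer that placebo participants would be given Theraworx. The documents do not support that. Risk and Benefits, item 1, speaks of randomisation to placebo, and item 6 separates the treated wrap from a placebo wrap. The sentence on the wrap can be read as describing the active product only. For the same reason, adding arms 2 and 3 to claim that 40 of 60 subjects are compromised would overstate the problem.

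**Conclusion.** The point holds as an internal inconsistency: the visit instructions are wrong as written for the foam-alone arm and disagree with Study Design on how foam is applied. If they were followed, the arm 1 versus arm 3 contrast could be lost or could be confounded with delivery method. The placebo arm faces only an ambiguous description.

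The choice of three arms is not criticised, and the text does not show that the trial is really a two-arm study. No effect on the results is quantified and no one is said to have received the wrong product.

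The conclusion rests on the protocol text alone. The consent pages and the attached data collection forms are not visible, and any separate participant instructions could contain arm-specific detail that reduces the practical risk. Correction is worthwhile because every hypothesis uses the affected contrast and the remedy is nearly free.

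**What to change.** Replace the two-group wording in Basic Information, item 3, and Research Activities, item 1, with the three-arm list from Study Design, item 2. Then give arm-specific supplies and instructions under Research Activities:

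- Arm 1: Theraworx foam, plus wrap.
- Arm 2: placebo foam, plus wrap, applied in the same way as in arm 1.
- Arm 3: Theraworx foam, no wrap supplied.

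Use one application method and amount in all arms; the two pumps rubbed into the thumb base in Study Design already serve. Delete the sentence on the saturated wrap, and reword the nightly instruction so that the 6 to 10 hours apply to the foam in all arms and to the wrap in arms 1 and 2 only.

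The cost is a wording amendment, with any participant instructions brought into line. Sample size, visits and staffing do not change.
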